### For patients randomized to radiation:

Patients will undergo CT imaging of chest/abdomen/pelvis at 1 month after the last treatment of radiation is completed. Subsequently, they will undergo CT imaging of chest/abdomen/pelvis every 3 months for 3 years, then every 6 months for 2 years per standard of care.

**For patients randomized to continue maintenance immunotherapy:** alone, they will undergo CT imaging of chest/abdomen/pelvis at 1 month after the 2nd cycle of protocol directed maintenance immunotherapy has been delivered. Subsequently, they will undergo CT imaging of chest/abdomen/pelvis every 3 months for 3 years, then every 6 months for 2 years per standard of care.

Should a patient be enrolled after starting maintenance immunotherapy and after their first 3 month followup scan, then they may be allowed to

switch to 6 months interval imaging at 3yrs from the end of chemo-immunotherapy, rather than a full 3 yrs from the date of randomization in accordance with standard of care. At discretion of treating oncologist.

If a patient, has suspicion of progression but requires closer interval followup than 3 months or additional imaging, this is allowable at the discretion of the treating physician. If ultimately, they are deemed to not have progressive disease, they would then resume the schedule listed in the study calendar above.

**8.4.2** Patients who progress on or after protocol directed therapy will be followed for survival only as per Appendix L without further protocol follow up requirements. This includes progression of the protocol treated tumors, non-protocol treated tumors and the development of new metastatic disease. Tumor progression will be determined by RECIST criteria.

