**14.2 Analysis of Secondary Objective**

The proportions with local control (LC) of SBRT-treated lesions, and overall survival (OS) parameter estimates, both secondary outcomes, will be first examined in simple univariate and bivariate analyses (e.g., means, medians, 85% confidence intervals around key parameter estimates.). LC will be assessed only in patients with at least 4-months of radiographic follow -up. The reason for specifying a minimum of 4 months follow-up to score LC was to avoid uncertainty associated with early transient radiographic changes within the high dose region; patients who died without a minimum of 4 months post-SBRT imaging study follow-up are not considered evaluable for LC but are evaluable for PFS and OS.

Data will be collected for planned subset analysis of in-field local control of irradiated sites, progression-free and overall survival according to (1) tumor histology (adenocarcinoma vs other histology) and (2) response to initial chemotherapy (response vs stable disease).

In all randomized patients, time to progression at known sites of disease, as well as time to development of new disease sites, and number of new disease sites will be collected.

Overall survival comparison between the two randomized groups will be assessed with methods analogous to PFS described above in 13.1. Additionally, we will also examine OS in the group of patients who were enrolled but not randomized; however, we will not conduct statistical comparisons of this group with either randomized group.

All safety measures, including acute and late toxicity, will be reported using descriptive statistics (mean, median, SD, proportions, and 95% confidence intervals). This will include calculating frequency/risk of adverse events by treatment site. Potential toxicities reported would include pneumonitis, esophagitis, chest wall pain, dermatologic toxicity, renal dysfunction, gastrointestinal toxicity including nausea, vomiting, and diarrhea, hepatotoxicity, and abdominal pain. These toxicities would be assessed according to site of irradiation by the treating physician and graded as per CTCAE 5.

A Randomized Trial of Consolidative Immunotherapy with vs without Thoracic Radiotherapy and / or Stereotactic Body Radiation Therapy (SBRT) after First-line Systemic Therapy for Metastatic NSCLC  
Wake Forest Baptist Comprehensive Cancer Center  
WFBCCC # 62718

Reference List

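### Section 14.2 reports local control as a proportion with no time point although protocol imaging stops at any progression, so histology and response subsets can differ with identical in-field risk

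*Combined protocol and SAP*

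**What the plan says.** Section 14.2 names "The proportions with local control (LC) of SBRT-treated lesions" as a secondary outcome. Together with overall survival, these "will be first examined in simple univariate and bivariate analyses (e.g., means, medians, 85% confidence intervals around key parameter estimates". The only time element is an evaluability rule: "LC will be assessed only in patients with at least 4-months of radiographic follow"-up. In line with that, "patients who died without a minimum of 4 months post-SBRT imaging study follow-up are not considered evaluable for LC". Four months is thus a minimum for entering the denominator, not the time at which LC is read.

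The next paragraph of 14.2 states: "Data will be collected for planned subset analysis of in-field local control of irradiated sites". It extends this to PFS and OS, takes histology and response versus stable disease as the subsets, and names no method. The paragraph after it says that, in all randomized patients, "time to progression at known sites of disease, as well as time to development of new disease sites" will be collected; no analysis of these times is tied to LC.

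On follow-up, Section 8.4.2 states: "Patients who progress on or after protocol directed therapy will be followed for survival only as per Appendix L without further protocol follow up requirements". It counts treated tumors, untreated tumors and new metastases alike as progression. Note 9 to the calendar in Section 8.1 repeats the rule. Kaplan-Meier, log-rank and proportional hazards methods are specified for PFS (14.1) and, by analogy, for OS (14.2), but not for LC.

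**The concern.** An in-field failure can be recorded only while the treated lesion is being imaged under the protocol. A lesion in a patient who progresses distantly at month 5 enters the proportion as controlled, exactly like a lesion imaged for five years. A subset that progresses elsewhere sooner is watched for less time, so it shows fewer in-field failures even if radiation held equally well in both.

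This is separate from the 4-month evaluability rule, which decides who is counted. Here the counted patients have unequal observation time that the proportion ignores.

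The mechanism is relevant to this trial. In the randomized trial of local consolidative therapy described in Section 1.1, 10 of the 13 failures in the local-therapy arm were distant only, so out-of-field progression may well be the usual reason that imaging ends. Response and histology are also on the plan's own list of PFS covariates in 14.1, so unequal imaging time between these subsets is plausible. At stake are the meaning of the overall LC figure and the direction of the subset contrast: a poorer-prognosis subset could look better controlled.

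**Working it through.** The plan gives no LC figure to reproduce, so the check is whether the stated measure stays equal between two subsets when their in-field hazard is equal.

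**Inputs**
- In-field risk *p*: Table 1 cites 0% to 15% with no time point. I use 5%, 12% and 15% as 12-month risks, the same in both subsets (assumption).
- Median time *m* from radiation to out-of-field progression or death: not given by subset. I use 6, 9, 12 and 20 months, exponential and independent of in-field failure (assumption).
- Follow-up *C*: 54 months of accrual and 5 years in total (Section 13.1) give 60 − 54 = 6 to 60 months, taken as uniform and counted from radiation (approximation).
- Evaluable: at least 4 months of imaging (14.2).
- Radiation arm: 112 × 2/3 ≈ 75 patients, split 37 and 38 (even split assumed).

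**Formula**
- λi = −ln(1 − p)/12; λo = ln 2/m; L = λi + λo.
- Imaging stops at the first of in-field failure, out-of-field event or C. Among evaluable patients, crude in-field failure = (λi/L) × E, where E = 1 − [exp(−2L) − exp(−56L)]/(54L).

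**Worked case, p = 12%** (λi = 0.01065)
- m = 6: λo = 0.1155, L = 0.1262, λi/L = 0.0844, E = 0.886; crude failure 7.5%.
- m = 12: λo = 0.0578, L = 0.0684, λi/L = 0.1557, E = 0.770; crude failure 12.0%.
- Gap 4.5 points, with the faster-progressing subset looking better.

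**Range** (crude in-field failure by m, then gap in points)

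| 12-month risk | m = 6 | m = 9 | m = 12 | m = 20 | 9 v 12 | 6 v 12 | 6 v 20 |
|---|---|---|---|---|---|---|---|
| 5% | 3.1% | 4.3% | 5.1% | 6.7% | 0.9 | 2.0 | 3.6 |
| 12% | 7.5% | 10.0% | 12.0% | 15.5% | 2.0 | 4.5 | 8.0 |
| 15% | 9.3% | 12.4% | 14.8% | 19.0% | 2.4 | 5.5 | 9.7 |

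With equal medians the gap is exactly zero. A simulation of 4,000 trials with staggered entry gave 2.0, 4.7 and 5.7 points for 6 v 12, in agreement. If every patient could be imaged for a full 60 months, the 6 v 12 gaps would be 3.1, 6.8 and 8.2 points. Whether an in-field failure before month 4 counts as evaluable is unstated; counting it changes the 6.8 to 5.9.

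**Against sampling error.** The simulation left about 22 to 32 evaluable patients per subset. At 12% failure with 22 and 29 patients, the standard error of a difference is √(0.12 × 0.88/22 + 0.12 × 0.88/29) = 9.2 points. With unequal medians (6 v 12, 8 v 15, 6 v 18), a Fisher test at 0.05 rejected in 0.3% to 7.7% of trials.

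**Does the remedy work?** Kaplan-Meier LC, censored at out-of-field progression or death and read 12 months after the 4-month landmark, averaged 0.95, 0.88 and 0.85 in both subsets at the three risks. A fixed time point alone is not enough. The 12-month cumulative incidence, (λi/L)(1 − exp(−12L)), at p = 12% is 6.6% for m = 6 and 8.7% for m = 12.

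**The case against.** Four points can be made for the plan.

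1. The subset method is not stated. The sentence on subsets only says that data will be collected, the proportions wording sits in a separate paragraph, and LC is there only first examined by simple summaries. Times to progression at known sites are collected, and Appendix K records the progression date and whether it lies inside the radiation field. This stands: a reader might infer that the plan prespecifies a crude subset comparison, and it does not. But the crude proportion is the only LC measure defined, and nothing directs the analyst elsewhere.

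2. A reader might infer that the subsets are bound to differ. The documents give no progression rates by histology or response, and with equal rates there is no gap. This stands; the effect is conditional.

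3. A reader might quote 9.3% versus 19.0% and say that failure doubles. That needs the top of the cited in-field range, read as a 12-month risk, with medians of 6 and 20 months. The radiation arm as a whole is planned around a median of about 15 months from the start of systemic therapy. For a patient randomized on day 180 (5.9 months) and irradiated 21 days later (0.7 months), that leaves 15 − 5.9 − 0.7 = 8.4 months, and more if randomized earlier. A contrast such as 9 versus 12 months is closer to this design.

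4. The gap is small against a standard error near 9 points, LC is absent from the objectives and outcomes in Sections 2 and 5, and no arm comparison depends on it. This limits the importance. It does not remove the error, which is systematic in direction, and the overall LC figure still has no time attached.

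**Conclusion.** The concern holds in conditional form. The only LC measure in the plan mixes in-field failure with length of imaging, has no time reference, and can differ between histology or response subsets when out-of-field progression or death differs, at identical in-field risk. The subset that progresses elsewhere sooner is flattered.

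The size is about 1 to 2.5 points for 9 versus 12 months, 2 to 6 for 6 versus 12, and 4 to 10 for the extreme 6 versus 20. It rests on assumed exponential, independent times, a common 12-month in-field risk of 5% to 15%, and the 4-month rule. None of the subset rates is in the documents.

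A reader might go further and infer a material inflation of false positives. The calculations do not support that: the rejection rate was mostly at or below 5% and reached 7.7% only in the most unequal simulated case. The matter is worth correcting because it biases a descriptive secondary estimate and the correction is cheap. The primary PFS comparison is unaffected.

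**What to change.** In Section 14.2, replace the crude proportion with a time-to-event analysis of in-field failure from the end of radiation, reported at fixed times such as 12 and 24 months. Base the histology and response comparisons on the cause-specific hazard of in-field failure, censoring at the last scan before out-of-field progression, death or end of follow-up. State the assumption that this censoring is independent of in-field failure.

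If cumulative incidence is also shown, treat out-of-field progression and death both as competing events. Describe it as absolute observed risk, not as a measure of how well radiation held in one subset against another.

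The cost is mainly wording and modest analysis. Scan dates are on Appendix G, and progression date and field status on Appendix K; no visit, scan or patient is added. Appendix G records target, non-target and overall response but not the status of each lesion, so some lesion-level scan dates may need abstraction. Intervals at later times will be wide, and the independent-censoring assumption cannot be verified from the data collected.

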**2.2 Secondary Objective(s)**

- 2.2.1 We plan to estimate overall survival in all patients and will compare overall survival of those randomized to radiation and consolidative immunotherapy against those receiving consolidative immunotherapy alone.
- 2.2.2 In patients who experience subsequent failures after initiating protocol directed therapy, we will assess whether these failures occurred at known or new sites of disease.
- 2.2.3 We plan to evaluate toxicity associated with the addition of consolidative radiation therapy to upfront chemoimmunotherapy followed by additional consolidative immunotherapy. This will include calculating rates of adverse events depending on treatment site. Potential toxicities reported would include pneumonitis, esophagitis, chest wall pain, dermatologic toxicity, renal dysfunction, gastrointestinal toxicity including nausea, vomiting, and diarrhea, hepatotoxicity, and abdominal pain. These toxicities would be assessed according to site of irradiation by the treating physician and graded as per CTCAE 5.

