**If randomized to consolidative radiation therapy then maintenance immunotherapy:**

Maintenance immunotherapy may NOT be delivered concurrently with consolidative radiation. Concurrently is defined as on the same day of any radiation treatment or on any day between the first and last treatment of radiation. Resumption of maintenance immunotherapy after completion of radiation therapy is at the discretion of the treating medical oncologist. They may resume maintenance immunotherapy as early as 24 hrs after the last radiation treatment, but resumption should be no later than 8 weeks from the last radiation treatment. If treatment related toxicities prohibit administration of maintenance immunotherapy, then restarting this therapy is at the discretion of the treating medical oncologist. In such cases, patients will remain on study until they experience progression or death. If they experience progression, patients will be followed for overall survival only per appendix L past the point of progression.

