## 6.0 Pembrolizumab

In order to maintain dose-intensity and cumulative dose-delivery, reasonable efforts should be made to minimize dose reductions and treatment delays. Any subject whose treatment is delayed should be evaluated on a weekly basis until adequate hematologic and non-hematologic parameters have been met. Patients may elect to delay doses of maintenance treatment for up to 3 weeks due to personal preference and this will not constitute a protocol deviation.

Toxicities may require the dose reduction of one or more of the study required medications. The investigator will carefully assess all treatment associated toxicities and, whenever possible, determine if the toxicities can reasonably be attributed to a single agent or a causal relationship with one of the agents can reasonably be ruled out. If appropriate, dose reductions should not affect the dose of other products.

CTC-AE measures will occur at each cycle of consolidation immunotherapy. Dose modifications and treatments for adverse events will be managed at the discretion of the treating physicians per their standard practice. Guidance statements regarding dose modifications and ae management are provided as suggestions for treating physicians but are not mandatory. Reasons for dose delays, dose modifications, or addition of steroid treatments must be documented by the treating physician.

- Toxicity grades are defined using the National Cancer Institute Common Terminology Criteria for Adverse Events (NCI-CTCAE) version 5.0
- Dose escalations are not allowed

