  - c. The schedule above is standard of care for imaging followup. Should a patient be enrolled after starting maintenance immunotherapy and after their first 3 month followup scan, then they may be allowed to switch to 6 months interval imaging at 3yrs from the end of chemo-immunotherapy, rather than a full 3 yrs from the date of randomization in accordance with standard of care. At discretion of treating oncologist.
7. Definition of 1 mo. or 30 day followup
  - a. For patients randomized to RT, this time point is considered 30 days +/- 14 days from end of all radiation therapy treatments
  - b. For patients randomized to immunotherapy alone, this time point is considered 30 days +/- 14 days from the end of the 2nd cycle of on protocol maintenance immunotherapy
8. Two tubes of whole blood may be collected at time of registration or any time prior to initiating any protocol directed therapy and at the 1 month follow up +/- 2 weeks.
9. If patients progress and are not eligible for randomization, or if they progress at any point on the study, they are only followed w appendix L for survival after the point of progression

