**Appendix L: Survival Form**

**Instructions:** Fill this form out at protocol indicated survival assessments

1. Last known Survival Status:  
 Alive  
 Dead  
 Lost to Follow-up: Date of last contact \_\_\_\_/\_\_\_\_/\_\_\_\_ (MM/DD/YYYY)
2. Expired Date \_\_\_\_/\_\_\_\_/\_\_\_\_ (MM/DD/YYYY)  
Is this an approximate date?  Yes  No
3. Last known Alive Date \_\_\_\_/\_\_\_\_/\_\_\_\_ (MM/DD/YYYY)
4. Survival Status source: \_\_\_\_\_  
*Instructions: Source can be EMR, obituary, family member etc. Phone call with patient  
Add to comments in WISER follow-up section*
5. Comment: \_\_\_\_\_

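### Toxicity is reported as proportions with no time basis while scheduled AE assessment stops at progression, so if radiation prolongs PFS its late and cumulative AE figures will tend to be higher at an equal AE rate

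*Combined protocol and SAP*

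**What the plan says.** Section 14.2 covers acute and late toxicity in one sentence: "All safety measures, including acute and late toxicity, will be reported using descriptive statistics (mean, median, SD, proportions, and 95% confidence intervals"). It names no person-time rate, cumulative incidence or fixed window. The one breakdown it spells out is by irradiated site: "This will include calculating frequency/risk of adverse events by treatment site". Objective 2.2.3 is wider: "We plan to evaluate toxicity associated with the addition of consolidative radiation therapy to upfront chemoimmunotherapy followed by additional consolidative immunotherapy".

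The study calendar (Section 8.1) schedules toxicity grading at 1 month, then every 3 months for 3 years and every 6 months for 2 years. Progression ends this. Section 8.4.2 states: "Patients who progress on or after protocol directed therapy will be followed for survival only as per Appendix L without further protocol follow up requirements". Footnote 9 of the calendar agrees: "they are only followed w appendix L for survival after the point of progression". Appendix L records vital status, dates and source, and has no AE item.

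Two other provisions bear on AE capture:
- Section 6.0: "CTC-AE measures will occur at each cycle of consolidation immunotherapy". Section 8.5 lists progression as an end of treatment, and Section 3.0 adds for the radiation arm that "Maintenance immunotherapy may NOT be delivered concurrently with consolidative radiation".
- Appendix R requires every AE in an enrolled patient to be entered in the database. Its window of 30 days after last treatment governs reporting to the monitoring committee.

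For local control and overall survival, Section 14.2 gives 85% intervals among its examples of summaries, without a reason. Safety gets 95%, and Section 13.1 sizes the trial at two-sided 0.05.

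**The concern.** How long a patient is actively assessed for AEs depends on when that patient progresses. PFS is the primary outcome and the one radiation is meant to lengthen. A proportion of patients who ever had an AE rises with observation time, so two arms with the same AE rate will show different proportions if one stays progression-free longer.

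Objective 2.2.3 asks what toxicity the addition of radiation brings, and in a randomised trial readers will answer that by comparing arms. If radiation works as planned, part of any excess in late or immune-related AEs would be an effect of longer observation, and a table of proportions cannot show how much. The 95% intervals do not reflect it either, because it is systematic rather than random.

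**Working it through.** **The plan's own figure.** 8/15 = 0.533, matching the stated hazard ratio of 0.53. With 112 patients allocated 2:1 (about 37 control, 75 radiation), exponential PFS, 54 months' accrual and 60 months in total, about 86.5 events are expected and power is 0.787, close to the stated 0.80. The sample size is not in question. Individual follow-up on that reading runs from 6 to 60 months.

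**Formula.** Let λ = ln 2 / median PFS, h = the AE hazard (assumed constant and equal in both arms; the documents give none), and s = h + λ. If assessment stops at progression or month c, the proportion with at least one recorded AE is F(c) = (h/s)(1 − exp(−s·c)). Averaged over c uniform on 6 to 60 months it is (h/s){1 − [exp(−6s) − exp(−60s)]/(54s)}.

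**Worked case, h = 0.02, staggered follow-up.**
- Control: λ = 0.0866, s = 0.1066, h/s = 0.1875; 0.1875 × (1 − 0.0913) = 0.170.
- Radiation: λ = 0.0462, s = 0.0662, h/s = 0.3021; 0.3021 × (1 − 0.1827) = 0.247.

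**Results, control vs radiation (gap in points).**

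| Observation | h = 1% per month | h = 2% per month |
|---|---|---|
| Staggered 6-60 months | 9.2% vs 13.8% (4.6) | 17.0% vs 24.7% (7.6) |
| AE accrual ends at 24 months | 9.3% vs 13.2% (3.8) | 17.3% vs 24.0% (6.7) |
| Both of the above | 8.8% vs 12.1% (3.3) | 16.3% vs 22.1% (5.8) |
| Staggered, plus 30 days after progression | 10.0% vs 14.4% (4.4) | 18.5% vs 25.8% (7.3) |
| All observed to progression or 60 months | 10.3% vs 17.2% (6.9) | 18.7% vs 29.6% (10.9) |
| Staggered, 3 months off both medians | 6.4% vs 12.1% (5.8) | 12.0% vs 21.9% (9.9) |
| Staggered, 6 months off both medians | 2.8% vs 10.1% (7.3) | 5.4% vs 18.4% (13.0) |

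The last two rows are needed because Sections 8.10 and 13.1 measure PFS from the start of first-line therapy, while randomisation comes after four cycles and up to day 180. If PFS were strictly exponential from the start, no subtraction would be due, so these rows are a sensitivity range. With medians of 8 vs 10 months the gap is 1.4 to 2.7 points; with equal PFS it is 0.

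**Early.** At 2% and the planned medians: 6.5% vs 7.0% by 4 months and 7.8% vs 8.5% by 5 months. With 6 months off both medians, the 5-month figures are 4.6% vs 7.9%, so an early window reduces the effect but does not always remove it.

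**Rates.** At 2%, staggered: 6.3 first events in 315 event-free patient-months vs 18.5 in 926, which is 0.020 in each arm. A single overall rate is not enough. With 4% per month for 3 months and 1% afterwards in both arms it gives 0.019 vs 0.016, while splitting at the change point gives 0.040 and 0.010 in each arm.

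**Latest first follow-up visit after randomisation.** Control: 21 days to start, 42 for two cycles, then 30. Radiation with 33 fractions, five a week assumed: 21 + 45 + 30. Adding 14 days (Section 8.1, footnote 7; Appendix F) gives days 107 and 110. Adding 56 days (the ±8 weeks stated after the calendar and in Section 8.4.1) gives days 149 and 152.

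**Grading frequency.** Immunotherapy may resume up to 8 weeks after radiation, so per-cycle grading can lapse for 8/3 = 2.7 cycles, or (33/5 + 8)/3 = 4.9 cycles including a 33-fraction course. This works in the opposite direction to the main effect.

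**85% level.** 1.440/1.960 = 0.734, so these intervals are 27% narrower than 95% ones.

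**The case against.** Several points on the other side are sound.

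- Section 14.2 specifies no toxicity comparison between arms, and its stated breakdown by treatment site applies only to irradiated patients. This stands: the comparison is an inference from objective 2.2.3.
- No test is affected, and the artefact is smaller than sampling error. At 2% per month the 95% half-width for the difference is 1.96 × √(0.170 × 0.830/37 + 0.247 × 0.753/75) = 0.156, about 16 points. This also stands. It limits the importance of the point but does not remove it, because the shift has a predictable direction if the trial succeeds.
- A reader might infer that no AE is recorded after progression. The documents do not support that: Appendix R's entry rule covers all AEs in enrolled patients, and its 30-day window limits reporting, not entry. What stops is scheduled assessment, so later events may be recorded but no visit is planned to find them.
- A reader might take 3-8 points, or 7-11, as limits on the distortion. They are not. Every AE hazard is assumed, and the medians have an earlier time origin than on-study AE observation.
- A reader might infer that the 85% level weakens the survival comparison. It appears in a list of examples for a first descriptive step, may be a typing error, and changes no estimate or test; the comparison of overall survival follows the PFS methods.

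**Conclusion.** The point holds as a cheap reporting improvement. Toxicity proportions without a time basis, combined with scheduled assessment that stops at progression, will tend to show more cumulative and late AEs in the radiation arm at an equal AE rate if radiation prolongs PFS. The direction follows from longer observation.

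The size rests on assumptions: equal constant AE hazards of 1-2% per month and exponential PFS. With medians of 8 vs 15 months applied from the start of on-study observation, the gap is about 3-8 points, or 7-11 if everyone is observed to progression or 60 months. With 3-6 months subtracted from both medians and staggered follow-up it is about 6-7 points at 1% and 10-13 at 2%. The documents do not support a claim that the primary analysis, or any test, is compromised. The 85% level is a minor inconsistency.

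**What to change.** Keep the proportions in Section 14.2 and add, by arm:

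1. AE risk in one fixed early window from randomisation, the same in both arms and meant to contain the first follow-up visit. First reconcile the two visit tolerances: about 4 months if ±14 days applies, about 5 months if ±8 weeks applies. Dose delays allowed in Section 6.0, or radiation to several sites in sequence, could still push some visits later.
2. AE rates per patient-month from randomisation to progression, death or last AE assessment, split at the end of that window. List AEs recorded after progression separately, so that events and patient-months cover the same period.

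State beside the table that scheduled AE assessment stops at progression and that per-cycle grading pauses during radiation; the window does not correct for the latter. Use 95% intervals for local control and overall survival, as for safety, or justify 85%.

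The cost is a few sentences and a small table. No new data are needed: the AE log (Appendix S) has start dates and Appendix K the progression date. The downsides are rates that are less intuitive than percentages, wider local control and survival intervals, and sparse control counts. At 2% per month with a 5-month split, about 2.9 control patients have a first event early and 3.4 later, against 6.4 and 12.1 with radiation, so more than two periods would be too thin.
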